8 INVESTIGATIONAL DRUG INFORMATION

8.1 OBI-833 (Globo H-CRM197)

Formulation:

OBI-833 is supplied as a sterile lyophilized powder drug product in single-use 2 mL amber borosilicate glass serum vials. Each vial contains 150 μ g Globo H linked with CRM197 along with potassium phosphate buffered saline, Sucrose, and polysorbate 80.

The physical appearance specification for the drug product is lyophilized cake/powder. The reconstituted solution of OBI-833 drug product is a clear liquid.

Supplier:

OBI-833 will be supplied by OBI Pharma, Inc.

Source and Pharmacology:

OBI-833 is a glycoconjugate comprised of a carbohydrate tumor antigen, Globo H, which is covalently linked to the carrier protein, an inactive and nontoxic form of diphtheria toxin (DT) called cross-reacting material 197 (CRM197).

Immunization of mice with Globo H-CRM197 (DT) induced antibodies reactive with Globo H, SSEA-3, and SSEA-4, suggesting that a Globo H-based vaccine will target tumor cells expressing Globo H, SSEA-3, and SSEA-4. More specifically, as Globo H, SSEA-3, and SSEA-4 are found to be expressed in human tissues of breast cancer, hepatocellular cancer (HCC), lung cancer, oral cancer, gastric and pancreatic cancers, it is postulated that the anti-Globo H, SSEA-3 and SSEA-4 antibodies generated from immunization of OBI-833/OBI-821 can target tumor cells in aforementioned cancer types.

8.2 **OBI-821**

Formulation:

OBI-821 is lyophilized powder/cake in individual 2 mL amber borosilicate glass serum vial containing 125 µg OBI-821, sodium phosphate buffered saline, and Trehalose.

Supplier:

OBI-821 will be supplied by OBI Pharma, Inc.

Source and Pharmacology:

OBI-821 is a saponin based adjuvant derived from the bark of the *Quillaja saponaria* Molina tree. OBI-821 is a purified saponin, which is structurally similar to descriptions found in the literature for another adjuvant, QS-21. OBI-821 exists as a mixture of isomers. The primary component is designated as OBI-821-V1A, with the balance being a group of closely related analogs.

OBI-821 has been shown to stimulate a variety of immunological activities including antigenspecific antibody to carbohydrate tumor antigen conjugated to a carrier protein. OBI-821 also augments the induction of major histocompatibility complex (MHC)-restricted class I cytotoxic T lymphocytes to subunit antigen vaccines, as well as antigen-specific cellular proliferation.

8.3 Clinical Trial Material (CTM) Supply, Packaging, Labeling and Storage

All CTM will be supplied by OBI Pharma, and must remain under adequate security, storage condition. Do not use any CTM after the expiration date, which is labeled on the investigational drug container.

Investigational Drug Supply

- OBI-833 (equivalent to 150 μg Globo-H) and OBI-821 (125 μg) are provided in separate single-use vials. OBI-821 is mixed with OBI-833 at the time of each injection (within 2 hours after mixing). Following the injections, the leftover OBI-833/OBI-821 mixtures are not recyclable.
- Each injection dose consists of a mixture of 100 μg OBI-821 and OBI-833 containing 10 μg, 30 μg, or 100 μg of Globo H equivalents. OBI-833 drug product is reconstituted in water and mixed with reconstituted OBI-821 immediately. The freshly combined OBI-833/OBI-821 mixture is administered by subcutaneous injection. See Appendix I for detailed procedure for preparation and mixing of OBI-833 and OBI-821 for injection.

Packaging and Labeling

• Packaging and the contents of the label will be in accordance with all applicable regulatory requirements.

Investigational Drug Storage

• OBI-833 and OBI-821 are provided in separate single-use vials. OBI-821 is to be mixed with OBI-833 at time of injections. The recommended storage temperature for both OBI-833 and OBI-821 drug product vials are between 2–8°C.

9 STUDY ENDPOINT

9.1 **Primary Endpoints**

The primary endpoint is safety and tolerability of OBI-833/OBI-821 assessed by adverse events, changes in laboratory values, and changes in vital signs and physical exam results.

9.2 Secondary Endpoints

- Immune response as assessed by anti-Globo H IgG and IgM production.
- Tumor response per RECIST 1.1 criteria.

9.3 Safety Assessment

- Toxicity and adverse events will be assessed by NCI CTCAE v4.0 following subcutaneous doses of OBI-833/OBI-821 immunization.
- Safety and toxicity will be assessed according to the dose of OBI-833/OBI-821 the subjects received and on all subjects who received at least one dose of OBI-833/OBI-821. Every effort should be made to follow up all subjects and all scheduled evaluations should be performed until study closure or the death of the subjects irrespective of withdrawals from the treatments.
- Any clinically significant abnormalities persisting at the end of the study/early termination will be followed by the investigator until resolution or until a clinically stable endpoint is reached.

9.4 Safety Variables

- Toxicity & adverse events (as assessed by NCI CTCAE v4.0).
- Safety laboratory examination (Urinalysis, hematology and serum chemistry).
- Vital signs (blood pressure, respiratory rate, pulse and temperature).
- Liver and renal functions.
- Physical exam.
- ECG.

10 RESPONSE CRITERIA

Criteria for Tumor Response by RECIST 1.1:

RECIST 1.1 will be used as the guideline for the analysis of this study. Images will be taken from the chest, abdomen and pelvis area. A Baseline/Screening tumor burden will be obtained by evaluating the entire organ systems included in the body systems imaged. This tumor burden will be categorized as either Measurable (Target Lesions) or Non-Measurable (Non-Target Lesions) (see Section 10.1). The purpose of establishing this Baseline/Screening is to allow for subsequent assessment of on-treatment response.

10.1 Definitions for Measurability of Tumor Lesions

Measurable:

Tumor lesions must be accurately measured in at least one dimension (longest diameter in the plane of measurement is to be recorded) with a minimum size of:

- 10 mm by CT scan (CT scan slice thickness recommended to be in between 2.5 mm and 5 mm).
- 10 mm caliper measurement by clinical exam (lesions which cannot be accurately measured with calipers should be recorded as non-measurable).
- 20 mm by chest X-ray.
- Malignant lymph nodes:

To be considered pathologically enlarged and measurable, a lymph node must be ≥ 15 mm in short axis when assessed by CT scan (CT scan slice thickness recommended to be in between 2.5 mm and 5 mm). At baseline and during follow-up, only the short axis will be measured and followed See also notes below on 'Baseline documentation of target and non-target lesions' for information on lymph node measurement. Tumor lesions situated in a previously irradiated area, or in an area subjected to other loco-regional therapy, are usually NOT considered measurable unless there has been demonstrated progression in the lesion.

Non-Measurable:

All other lesions, including small lesions (longest diameter <10 mm or pathological lymph nodes with ≥10 to <15 mm short axis) as well as truly non-measurable lesions.

Lesions considered truly non-measurable include: leptomeningeal disease, ascites, pleural or pericardial effusion, inflammatory breast disease, lymphangitic involvement of skin or lung, abdominal masses/abdominal organomegaly identified by physical exam that is not measurable by reproducible imaging techniques.

10.2 Recording Tumor Lesions

When more than 1 measurable lesion is present at baseline all lesions up to a maximum of **5 lesions** total (and a maximum of **2 lesions** per organ) representative of all involved organs should be identified as target lesions and will be recorded and measured at baseline (this means in instances where subjects have only 1 or 2 organ sites involved a maximum of 2 and 4 lesions respectively will be recorded).

A sum of the diameters (longest for non-nodal lesions, short axis for nodal lesions) for all target lesions will be calculated and reported as the baseline sum diameters. If lymph nodes are to be included in the sum, then as noted above, only the short axis is added into the sum. The baseline sum diameters will be used as reference to further characterize any objective tumor regression in the measurable dimension of the disease.

All other lesions (or sites of disease) including pathological lymph nodes should be identified as **non-target lesions** and should also be recorded at baseline. Measurements are not required and these lesions should be followed as 'present', 'absent', or in rare cases 'unequivocal progression'.

In addition, it is possible to record multiple non target lesions involving the same organ as a single item on the case record form (e.g., 'multiple enlarged pelvic lymph nodes' or 'multiple liver metastases').

10.3 Response Evaluation

Target Lesions

- Complete Response (CR): Disappearance of all target lesions. Any pathological lymph nodes (whether target or non-target) must have reduction in short axis to <10 mm.
- Partial Response (PR): At least a 30% decrease in the sum of diameters of target lesions, taking as reference the baseline sum diameters.
- Stable Disease (SD): Neither sufficient shrinkage to qualify for PR nor sufficient increase to qualify for PD, taking as reference the smallest sum-diameters while on study. Measurements must have met the SD criteria at least once after study entry at a minimum interval of 6 weeks.
- Progressive Disease (PD): At least a 20% increase in the sum of diameters of target lesions, taking as reference the smallest sum on study (this includes the baseline sum if that is the smallest on study). In addition to the relative increase of 20%, the sum must also demonstrate an absolute increase of at least 5 mm. (Note: the appearance of one or more new lesions is also considered progression).
- At each time point, the presence or absence of new lesions will be assessed.

Non-Target Lesions

- Complete Response (CR): Disappearance of all non-target lesions and normalization of tumor marker level. All lymph nodes must be non-pathological in size (<10 mm short axis).
- Stable Disease (SD): Persistence of one or more non-target lesion(s) and/or maintenance of tumor marker level above the normal limits.
- Progressive Disease (PD): Unequivocal progression of existing non-target lesions. (Note: the appearance of one or more new lesions is also considered progression).

Target Lesions	Non-Target Lesions	New Lesions ¹	Time Point Response
CR	CR	No	CR
CR	SD	No	PR
CR	UE	No	PR^2
PR	UE	No	PR^2
PR	CR	No	PR
PR	SD	No	PR
SD	UE	No	SD
SD	CR	No	SD
SD	SD	No	SD
PD	ANY	Yes/No	PD
ANY	Unequivocal PD/PD	Yes/No	PD
ANY	ANY	Yes	PD
UE	Non-PD	No	UE
CR	NA^4	No	CR
PR	NA^4	No	PR
SD	NA^4	No	SD
NA ³	SD	No	SD
NA ³	CR	No	CR
NA ³	UE	No	UE
NA ³	NA ⁴	No	UE

Table 3Overall Response Table

¹ Identification of new lesions at a post-baseline time point will result in time point response of PD. If an identified new lesion subsequently becomes UE, the time point response will be recorded as PD unless the new lesion has proven to have resolved.

² If a non-target lesion is classified as UE, a designation of PR may be assigned based on information from the target lesions.

³ No target lesions identified at baseline.

- ⁴ No non-target lesions identified at baseline.
- ⁵ CR = complete response, PR = partial response, SD = stable disease, PD = progressive disease, UE = unable to evaluate, and NA = not applicable.

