3 ELIGIBILITY CRITERIA

3.1 Inclusion Criteria

- 1. Subjects \geq 21 years of age
- 2. [Dose Escalation Phase]

Histologically or cytologically confirmed diagnosis of gastric, lung, colorectal or breast cancer on file

[Cohort Expansion Phase]

Histologically or cytologically confirmed diagnosis of Globo H-positive NSCLC

3. [Dose Escalation Phase]

Subjects with recurrent or metastatic incurable disease that failed to respond to at least one line of standard anticancer therapy and for which standard treatment is no longer effective or tolerable.

[Cohort Expansion Phase]

Subjects with metastatic NSCLC who have achieved stable disease (SD), or partial response (PR) status after at least 1 regimen of anticancer therapy (i.e., chemotherapy, or targeted therapy, or PD-1/PD-L1 antagonists either alone or in combination), and there are no standard treatments available except permitted Target or PD-1/PD-L1 therapies as listed in section 7.1 (i.e., add on with first line ongoing Targeted therapy or PD-1/PD-L1 therapy).

- 4. Measurable disease (i.e., present with at least one measurable lesion per RECIST, version 1.1 [Eisenhauer 2009]).
- 5. [Dose Escalation Phase]

No known central nervous system (CNS) metastases or neurological symptoms possibly related to active CNS metastasis in Dose Escalation Phase.

[Cohort Expansion Phase]

Subjects with asymptomatic CNS metastases for at least four weeks before study drug treatment

- 6. Performance status: $ECOG \le 1$
- 7. Organ Function Requirements Subjects must have adequate organ functions as defined below:
 - AST/ALT \leq 3X ULN (upper limit of normal)
 - $AST/ALT \le 5X$ ULN [with underlying liver metastasis]
 - Total bilirubin $\leq 2.0 \text{ X ULN}$
 - Serum creatinine ≤ 1.5 X ULN
 - ANC $\geq 1500 / \mu L$
 - Platelets > $100,000/\mu L$
- 8. Subjects of child-bearing potential must agree to use acceptable contraceptive methods during treatment and until the end of the study. Subject not of childbearing potential (i.e., permanently sterilized, postmenopausal) can be included in study. Postmenopausal is defined as 12 months with no menses without an alternative medical cause.
- 9. Ability to understand and the willingness to sign a written informed consent document according to institutional guidelines.

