For 100 μ g dose cohort (Cohort 3), firstly three subjects will be enrolled in this cohorts. If one out of the first three Cohort 3 subjects develops a DLT, an additional three subjects will be further enrolled. If none of the first three or less than 2 of the 6 subjects experience DLT at the 100 μ g dose level, then this dose will be maximum dose for escalation phase. If more than 1 of 6 subjects experience DLT at this dose level, study will be suspended temperately and DSMB will review safety data to recommend if the study should be de-escalate to 30 μ g to complete a maximum of 6 subjects.

Upon the completion of 5 injections of OBI-833/OBI-821 in subjects in the dose escalation phase, OBI Scientific Committee justified safety, efficacy and immune response data of all the dose escalation phase subjects and recommend 30 µg dose of OBI-833 for cohort expansion.

OBI Scientific Committee also examined the data of all the dose escalation phase subjects and preclinical efficacy data to evaluate the type of cancers to benefit from OBI-833/OBI-821 treatment. OBI Scientific Committee determined that lung cancer (Non-Small Cell Lung Cancer) subjects with SD or PR tumor status are to be enrolled for preliminary antitumor activity evaluation. Up to 14 subjects are to be enrolled in the cohort expansion phase.

The total number of subjects to be enrolled in the study is thus flexible: a maximum number of 18 subjects can be enrolled in the dose escalation phase; and a maximum number of 14 subjects can be enrolled in the cohort expansion phase. A maximum of total 32 subjects can be enrolled in this Phase I study.

Dose modification may be considered, as justified by emerging safety data. Subject tumor biopsy/tissue samples will be collected at Week 1 using fresh prepared or paraffinated material from original surgery specimens to test for expression level of Globo H, SSEA-3, SSEA-4 and PDL-1 for data analysis purpose. IHC data is not for eligibility criteria for Dose Escalation Phase but only Globo-H⁺ NSCLC subjects will be enrolled in Cohort Expansion Phase.

Subjects who are eligible for participation in this study will be enrolled into the dose cohort that is open at the time the subject is registered for enrollment in Dose Escalation Phase.

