- Conduct routine urinalysis pH, protein, glucose, specific gravity, ketone, bilirubin, and urobilinogen. Analysis of urinary sediments (RBC, WBC, epithelial casts, hyaline casts, and bacterial) is optional.
- Conduct hematology test includes hemoglobin, hematocrit, WBC, RBC, platelet, differentials, RF and ESR.
- Conduct serum chemistry analysis includes sodium, potassium, chloride, calcium, magnesium, BUN, creatinine, ALT, AST, alkaline phosphatase, total protein, albumin, total bilirubin, LDH, amylase, lipase, cholesterol, triglycerides, cortisol, T3, T4, free T4, and TSH.
- Conduct HBV (e.g., HBsAg, HBeAg, and if clinically indicated, HBcAb and/or HBV DNA), HCV (e.g., anti-HCV) testing. Conduct HIV testing if no historical data are available. Optional tests (e.g., viral load) can be ordered based on lab test results and Investigator's clinical judgment for suspected active infection on follow-up visits. Antiviral agents are allowed for the treatment and management of viral infections. However, interferon therapy is not allowed, and if indicated, the subject needs to be excluded from the study.
- Perform 12-Lead ECG.
- Perform Tumor Assessment:
 - Full body CT scans (chest, abdomen, and pelvis) will be performed at screening and used as the baseline scan. If full body CT scan has been performed within 4 weeks of the screening exam (the date consent form sign by patient), then this previously performed scan can be used as the baseline scan.
 - To identify and record lesions to be evaluated for response based on RECIST 1.1 criteria.
 - Imaging will be assessed by the study site radiologist or delegated investigators.
 - For cohort expansion phase, an interval of at least 6 weeks is required for Stable Disease (SD) status; an interval of at least 4 weeks is required for Partial Response (PR) status.
- Record use of concomitant medications.
- Perform re-testing of lab assessments: a re-test may be allowed after 1 week (or by Investigators' judgment) from the initial lab test to re-confirm the subject's organ function or condition. However, the assessment needs to be conducted within the specified screening period prior to first dosing of the investigational drug.
- Perform pre-treatment tumor-specific antigen testing: CEA and CYFRA21-1 for all enrolled subjects in selected sites.

• Collect blood samples for exploratory analysis of the B/T cell immunogenomic and Ex vivo immunogenicity analysis in selected Taiwan sites.

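### Section 10.3 states no confirmation for on-study PR/CR, and the scope of the 4-week PR interval in the screening lists of Section 5.1 is unclear

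*Protocol*

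**What the plan says.** Section 10.3 gives the on-study criteria. For PR: "Partial Response (PR): At least a 30% decrease in the sum of diameters of target lesions, taking as reference the baseline sum diameters". For CR: "Complete Response (CR): Disappearance of all target lesions", with pathological nodes reduced below 10 mm in short axis. Table 3 combines target, non-target and new lesions into a time-point response. Neither place mentions a repeat assessment for PR or CR. Stable disease, in the same section, carries a minimum interval of 6 weeks after study entry.

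Section 5.1 says, for the cohort expansion phase, "an interval of at least 4 weeks is required for Partial Response (PR) status", alongside a 6-week interval for stable disease. The line stands in both screening lists and nowhere else. It names neither entry status nor on-study response.

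Inclusion criterion 4 asks that a subject "present with at least one measurable lesion per RECIST, version 1.1", and Section 10.1 sets the CT minimum at 10 mm (15 mm short axis for nodes). Inclusion criterion 3 brings expansion subjects in with stable disease or PR already achieved. Section 5.1 has images read by the site radiologist or delegated investigators. Section 4.1 says that up to 14 such subjects "are to be enrolled for preliminary antitumor activity evaluation". Tumor response is a secondary endpoint (Section 9.2), and no hypothesis is tested (Section 12.1). Expansion scans fall at Weeks 12 and 24, then every 8 weeks (Section 5.4).

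**The concern.** Two things are unsettled. First, nothing in the protocol separates a response seen once from a response that persists. A subject whose only target lesion measures 10 mm at baseline meets PR at 7 mm, a fall of 3 mm, and each further scan is another opportunity to cross that line once. A lesion that qualified because it measured at least 10 mm also tends to have been over-measured at baseline, which tilts later readings downward. Expansion subjects already have stable disease or PR, so small residual lesions are plausible, although no document describes baseline tumor burden.

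Second, the 4-week line can be read two ways. If it concerns entry status, PR at entry is subject to an interval that Section 10.3 does not require for PR as an endpoint. If it concerns on-study response, Section 10.3 omits it. A site reader and a programmer could apply different rules.

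The expansion has no control arm in which false responders would also appear. One response among 14 is 1/14 = 7 percentage points.

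**Working it through.** The protocol states no response rate, power or threshold, so there is no planned figure to reproduce. The question is how often a truly unchanged tumor would meet the PR criterion.

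**Inputs from the protocol.** PR when the follow-up sum is at most 0.7 × the baseline sum (10.3); smallest CT-measurable non-nodal lesion 10 mm (10.1); one lesion sufficient (3.1); scans at Weeks 12, 24, 32, 40 and 48 taken as five follow-ups (5.4); progression at a rise of at least 20% and 5 mm over the smallest sum (10.3); at most 14 subjects (12.2).

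**Assumptions, not in the protocol.** True size constant; independent normal measurement error per lesion and scan with standard deviation s = 0.5, 1.0, 1.5 or 2.0 mm; true sizes spread evenly over the range shown.

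**Analytic check, one scan.** For a true 10 mm lesion, baseline B and follow-up Y both have mean 10 and standard deviation s. Then Y − 0.7B has mean 10 − 7 = 3 and variance s²(1 + 0.49), so P(PR) = Φ(−3 / (s√1.49)). This gives about 0%, 0.7%, 5.1% and 11% for s = 0.5, 1.0, 1.5 and 2.0. Requiring a baseline measurement of at least 10 mm raises these to about 0%, 1.4%, 9.4% and 19%.

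**Simulation, five scans.** Each baseline lesion must measure at least 10 mm, and follow-up stops at progression. Unconfirmed means PR at any scan; confirmed means PR at two consecutive scheduled scans. Cells show unconfirmed / confirmed chance per subject.

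| Target lesions, true size | s = 0.5 mm | s = 1.0 mm | s = 1.5 mm | s = 2.0 mm |
|---|---|---|---|---|
| one, 8–12 mm | 0 / 0 | 5% / 0.4% | 28% / 5% | 51% / 13% |
| one, 10–20 mm | 0 / 0 | 0.5% / 0% | 5.5% / 0.5% | 16% / 2% |
| two, 8–15 mm | 0 / 0 | 0.1% / 0% | 3% / 0.2% | 13% / 2% |
| three, 10–30 mm | 0 / 0 | 0 / 0 | 0 / 0 | at most 0.1% / 0 |

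**Cohort level.** If all 14 subjects had one 10–20 mm lesion, the chance of at least one false PR is 1 − (1 − p)^14:

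- s = 1.0 mm: 1 − 0.995^14 = 7% unconfirmed; about 0% confirmed.
- s = 1.5 mm: 1 − 0.945^14 = 55% unconfirmed; 1 − 0.995^14 = 7% confirmed.
- s = 2.0 mm: 1 − 0.84^14 = 91% unconfirmed; 1 − 0.98^14 = 25% confirmed.

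This is an upper-end case, because it gives every subject a minimal tumor burden. With two 10–20 mm lesions each and s = 1.5 mm, the unconfirmed figure is about 5%.

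**Feasibility of confirmation.** Consecutive scheduled scans are 24 − 12 = 12 weeks apart and then 8 weeks apart, so the next scan always meets a 4-week minimum.

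**The case against.** A reader might infer that the protocol counts a responder from a single scan. It does not say so. Table 3 defines a response per time point, and no section says how time points become a subject-level response or a rate. That derivation is commonly left to the statistical analysis plan, which is not at hand. Section 10 also adopts RECIST 1.1 by reference. Silence on confirmation is therefore not an error in itself. This stands.

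A reader might also infer that PR at entry is definitely held to a stricter rule than PR on study. Its place under screening favors that reading, but the line does not say so, and the paired 6-week figure is the one Section 10.3 uses for stable disease on study. It also speaks of an interval, not of a repeat scan. Only the ambiguity is established.

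Two further inferences fail. One sets the 3 mm fall against the recommended CT slice thickness. Section 10.1 measures the longest diameter in the plane, so slice thickness does not show that a 3 mm in-plane change is noise. The other contrasts PR with progression, where "the sum must also demonstrate an absolute increase of at least 5 mm", and asks for a similar floor in millimeters for response. A floor has no meaning for CR, which requires disappearance, and it is not needed once response is confirmed.

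On consequence, response is secondary and descriptive, drives no stated decision, and is observed alongside permitted EGFR/ALK inhibitors, bevacizumab and PD-1/PD-L1 inhibitors (Section 7.1). Section 10.2 also makes all measurable lesions targets, up to five in total and two per organ, so only subjects with very limited disease have a single target. These points limit the weight of the concern. They do not remove the unclear interval or the benefit of a simple confirmation rule.

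**Conclusion.** The point holds as a clarification and a cheap improvement, and should be rated no higher than that. The protocol leaves open whether the 4-week PR interval applies on study and states no confirmation for PR or CR. In a single-arm, locally read group of at most 14, confirmation lowers the false-PR chance for a subject with one 10–20 mm lesion roughly tenfold at an error of 1.5 mm (5.5% to 0.5%) and about eightfold at 2.0 mm (16% to 2%).

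The size rests on an assumed measurement error, independent errors, no true change and five scans. It matters for one or two small lesions with an error of about 1–1.5 mm or more. It is negligible at 0.5 mm or with three larger lesions. The calculation concerns PR; noise of this kind would rarely produce CR.

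A reader might go on to treat a confirmed response as evidence of OBI-833 activity. Confirmation reduces measurement noise only. With the permitted concomitant therapies it does not attribute the response to the vaccine.

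**What to change.** - **Section 10.3:** state that a subject is counted as a confirmed responder only if PR or CR is met again at the next scheduled scan, at least 4 weeks after the first. The stated minimum prevents an early unscheduled scan from serving as confirmation.
- **Reporting:** present confirmed response for the secondary endpoint and list unconfirmed responses separately.
- **Section 5.1:** state whether the 4-week PR and 6-week stable-disease intervals refer to entry status under inclusion criterion 3.

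The cost is one sentence in each of the two sections and one extra table column, with no added scans, visits or subjects. The response rate may come out slightly lower, and a true response first seen at a subject's last scan stays unconfirmed. The separate listing keeps such cases visible.
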